9.2.5 Assessment of Vertebral Fracture

1) Surveillance items

Vertebral fracture before the start of Benet treatment (baseline) will be confirmed, and the date of radiography, radiographic location, and location of vertebral fracture will be entered into the CRF. Then, the presence or absence and location of new vertebral fracture, presence or absence of worsening of prevalent vertebral fracture, and presence or absence of apparent trauma during treatment and at the end of the observation period (or discontinuation of treatment) relative to baseline will be entered into the CRF.

2) Time points of surveillance

At the start of Benet treatment, 12, 24, and 36 months after the start of treatment (or discontinuation of treatment), and when vertebral fracture is suspected during the observation period

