5.4. Handling of Time Points of Assessment

Data within the permissible range as shown below will be employed.*

If there are multiple pieces of data within the permissible range, data on the day closest to the nominal day will be employed. If deviation is the same before and after the nominal day, the latest data will be employed.

Data collected up to the end date of Benet/Actonel treatment* + 30 days will be employed for bone

turnover markers and low back pain, and data collected up to the end date of Benet/Actonel treatment* + 90 days will be employed for the other endpoints. For patients with interruption of treatment, no data collected after 3 consecutive months (90 days) of interruption will be used for (efficacy) analysis.

At the final assessment, the latest available data (excluding data before the start of treatment) will be employed.

The start day of Benet/Actonel treatment is designated as Day 1, and the previous day as Day -1.

* Specified in Section 5.5, “Derived Variables”

<Time points of assessment of bone turnover markers and low back pain>

| Time point of assessment | Permissible range | Nominal day |
|-------------------------------|-------------------|-------------|
| Before the start of treatment | Days -30 to 1 | Day 1 |
| Month 3 | Days 2 to 135 | Day 90 |
| Month 6 | Days 136 to 270 | Day 180 |
| Month 12 | Days 271 to 450 | Day 360 |
| Month 18 | Days 451 to 630 | Day 540 |
| Month 24 | Days 631 to 810 | Day 720 |
| Month 30 | Days 811 to 990 | Day 900 |
| Month 36 | Days 991 to 1170 | Day 1096 |
| Final assessment | Days 2 to 1170 | - |

<Time points of assessment of bone mineral density>

| Time point of assessment | Permissible range | Nominal day |
|-------------------------------|-------------------|-------------|
| Before the start of treatment | Days -90 to 30 | Day 1 |
| Month 3 | Days 31 to 135 | Day 90 |
| Month 6 | Days 136 to 270 | Day 180 |
| Month 12 | Days 271 to 450 | Day 360 |
| Month 18 | Days 451 to 630 | Day 540 |
| Month 24 | Days 631 to 810 | Day 720 |
| Month 30 | Days 811 to 990 | Day 900 |
| Month 36 | Days 991 to 1170 | Day 1096 |
| Final assessment | Days 31 to 1170 | - |

<Time points of assessment of height>

| Time point of assessment | Permissible range | Nominal day |
|--------------------------|-------------------|-------------|
| | | |

| | | |
|-------------------------------|------------------|----------|
| Before the start of treatment | Days -90 to 1 | Day 1 |

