| Flag for previous treatment | A drug deemed as previous treatment is identified. Previous treatment being used after the start of Benet/Actonel treatment is also identified with a flag for concomitant medication. |
| Flag for concomitant medication | A drug deemed as concomitant medication is identified. Concomitant medication that has been used since before the start of Benet/Actonel treatment is also identified with a flag for previous treatment. |
| Flag for osteoporosis drug | An osteoporosis drug is identified. |
| Flag for anti-inflammatory analgesic | An anti-inflammatory analgesic is identified. |
| Flag for cardiovascular drug | A cardiovascular drug is identified. |
| Flag for central nervous system drug | A central nervous system drug is identified. |
| Flag for antidiabetic | An antidiabetic is identified. |
| Flag for digestive system drug | A digestive system drug is identified. |
| Flag for other drug | Other drug not listed above is identified. |
| Flag for Benet/Actonel 2.5 mg | A drug that is Benet/Actonel 2.5 mg is identified. |
| Flag for Benet/Actonel 17.5 mg | A drug that is Benet/Actonel 17.5 mg is identified. |
| Flag for bisphosphonate other than Benet/Actonel | A bisphosphonate other than Benet/Actonel is identified. |
| Flag for calcium | A drug that is calcium is identified. |
| Flag for vitamin D | A drug that is vitamin D is identified. |
| Flag for osteoporosis drug not listed above | A drug that is an osteoporosis drug not listed above is identified. |
| Flag for steroid | A drug that is a steroid is identified. |
| Flag for parathyroid hormone | A drug that is a parathyroid hormone is identified. |
| Flag for anti-RANKL | A drug that is an anti-RANKL monoclonal antibody is |

| Derived variable | Description |
|--|--|
| monoclonal antibody | identified. |
| Number of days to measurement (days) | Number of days from the start date of Benet/Actonel treatment to the date of measurement of the relevant endpoint “Date of measurement” - “start date of Benet/Actonel treatment” + 1; or “date of measurement” - “start date of Benet/Actonel treatment” if the date of measurement is earlier than the start date of Benet/Actonel treatment |
| Time point of assessment (for analysis) | Time points of assessment of bone turnover markers, low back pain, bone mineral density, and height are reallocated for analysis as specified in Section 5.4, “Handling of Time Points of Assessment.” |

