6.3.1. Incidence of Vertebral Fracture

| | |
|---------------------|--|
| 1) Analysis set | Patients evaluated for efficacy with dates of pre- and post-treatment ^{*1} radiography Patients evaluated for vertebral fracture |
| 2) Chart plan | Table 3-1-1-1 Table 3-1-1-2 Table 3-1-1-3 Table 3-1-1-4 Table 3-1-1-5 Table 3-1-1-6 Table 3-1-2-1 Table 3-1-2-2 Table 3-1-2-3 Table 3-1-2-4 Table 3-1-2-5 Table 3-1-2-6 |
| 3) Analysis items | New vertebral fracture or worsening of prevalent fracture New vertebral fracture or worsening of prevalent fracture <non-traumatic> New vertebral fracture New vertebral fracture <non-traumatic> Worsening of prevalent fracture Worsening of prevalent fracture <non-traumatic> |
| 4) Analysis methods | For the time to the first onset of the analysis item, the point estimate of cumulative incidence, standard error, and 95% confidence interval will be calculated using the Kaplan-Meier method, and the number of relevant patients (number of patients at risk), cumulative number of patients with |

the analysis item, and cumulative number of censored patients at Month 6 (Day 180), Month 12 (Day 360), Month 18 (Day 540), Month 24 (Day 720), Month 30 (Day 900), and Month 36 (Day 1096) will be calculated. In addition, a Kaplan-Meier curve will be plotted with the cumulative incidence (%) on the vertical axis and the time (months) on the horizontal axis. The number of relevant patients (number of patients at risk) will be presented under the time (months).

The time to the first onset of the analysis item is defined as time from the start date of Benet/Actonel treatment to the earliest date of radiography with a diagnosis of the analysis item. Patients with no analysis item will be censored at the latest date of radiography with no evidence of the analysis item.^{*2}

No radiographic data collected after the end date of Benet/Actonel treatment + 90 days or after 3 consecutive months (90 days) of interruption in patients with interruption of treatment will be used for analysis.

*1 Range of assessment before and after treatment

- Before treatment: before the start of Benet/Actonel treatment defined as Days -90 to 1
- After treatment: before the end date of Benet/Actonel treatment + 90 days, and before 3 consecutive months (90 days) of interruption in patients with interruption of treatment

*2 The date of radiography with no evidence of the analysis item is defined as follows for each analysis set:

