6.3.3. Incidence of Vertebral Fracture Event at Each Time Point of Assessment

| | |
|---------------------|--|
| 1) Analysis set | Patients evaluated for vertebral fracture |
| 2) Chart plan | Table 3-3-1 Table 3-3-2 |
| 3) Analysis items | New vertebral fracture or worsening of prevalent fracture New vertebral fracture or worsening of prevalent fracture <non-traumatic> |
| 4) Analysis methods | The number of relevant patients, observed person·years, number of patients with the first onset of the analysis item, and incidence rate (number of patients with event/100 person·years) in the range of assessment at each time point of assessment (see below) will be calculated, and the ratio of incidence rate at each time point of assessment relative to Month 6 and its 95% confidence interval will be calculated. Handling of onset day of the analysis item and data for analysis will be as specified in Section 6.3.1, “Incidence of Vertebral Fracture.” |

Observed person·years: (1)+2)) ÷ 12

1): (Number of patients with radiography, no event, and no censoring in the range of assessment at each time point of assessment) \times 6

A patient with no radiography at the relevant time point of assessment, but with valid radiography at any later time point will be counted at the relevant time point of assessment.

2): Total time (months) from the start date of assessment to event or censoring in the range of assessment at each time point of assessment for patients with event or censoring

Incidence rate: (number of patients with event \div observed person-years) \times 100

Range of assessment at each time point of assessment

| Time point of assessment | Range of assessment |
|--------------------------|---------------------|
| Month 6 | Days 2 to 180 |
| Month 12 | Days 181 to 360 |
| Month 18 | Days 361 to 540 |
| Month 24 | Days 541 to 720 |
| Month 30 | Days 721 to 900 |
| Month 36 | Days 901 to 1096 |

No radiographic data collected after the end date of Benet/Actonel treatment + 90 days or after 3 consecutive months (90 days) of interruption in patients with interruption of treatment will be handled as data in the range of assessment (not used for analysis).

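### SAP 6.3.1 reads the vertebral fracture curve 5–12 days before the 12- and 24-month films are due, so Month 12 incidence is too low unless films run early or nearly all fractures are found by symptoms

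*SAP*

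**What the plan says.** Vertebral fracture incidence is the primary endpoint (Protocol 10.5.1). Protocol 9.2.5 calls for films at the start of treatment and then "12, 24, and 36 months after the start of treatment (or discontinuation of treatment), and when vertebral fracture is suspected".

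SAP 5.1 section 6.3.1 sets the event time at the "earliest date of radiography with a diagnosis of the analysis item". On censoring it says: "Patients with no analysis item will be censored at the latest date of radiography with no evidence of the analysis item". Cumulative incidence, standard error and 95% confidence interval come from Kaplan-Meier, and the read-outs include "Month 12 (Day 360), Month 18 (Day 540), Month 24 (Day 720), Month 30 (Day 900), and Month 36 (Day 1096").

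Section 5.4 fixes the day count: "The start day of Benet/Actonel treatment is designated as Day 1, and the previous day as Day -1". It gives markers, low back pain and bone mineral density a Month 12 window that spans the due date: "Month 12 | Days 271 to 450 | Day 360". Section 5.5 lists what is mapped to visits: "Time points of assessment of bone turnover markers, low back pain, bone mineral density, and height are reallocated for analysis". Vertebral films are not in that list. Section 6.3.3 takes its onset dates from 6.3.1 and has a range "Month 18 | Days 361 to 540".

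**The concern.** A fracture without symptoms enters the curve only when a film is taken. If the film due at 12 months normally comes after the Month 12 read-out, most patients are in the risk set at Day 360 while their silent first-year fractures are still uncounted. The estimate is then too low, and its confidence interval is centred in the wrong place. The same applies at Day 720.

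Section 6.3.3 repeats the mismatch. Its Month 12 range ends at Day 360, so an on-time Day 366 film counts under 'Month 18' and a Day 731–732 film under 'Month 30' (Days 721 to 900). That also disturbs the rate ratios against Month 6.

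At stake are the early figures for the primary endpoint, which the SAP reports with intervals.

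**Working it through.** **Inputs from the documents.** Film schedule, event and censoring rule, read-out days and day count as above. Registration from May 2013 to 31 October 2014 (Protocol 8.0). Dropout 50%, about 250 patients to analyse (Protocol 3.2). The plan gives no expected fracture rate. Its only related figure is the sample size, 250/(1 − 0.50) = 500, which reproduces.

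**Assumed.** Fracture rate; film dates normal around a centre, SD 14 or 30 days; share of fractures found promptly (filmed within 14 days); half of dropouts filmed unless stated.

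**Step 1: due days.** All 549 possible start dates from 1 May 2013 to 31 October 2014 were counted forward. The anniversaries fall 365, 730 or 731, and 1096 elapsed days after the start, which is Day 366, 731/732 and 1097 with the start as Day 1. On either count, on-time films fall 5–6 days after the Day 360 read-out, 10–12 days after Day 720, and 0–1 day after Day 1096.

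**Step 2: films in hand at the read-out (films centred on the due date).** Allowing half a day for whole-day dates:
- Day 360, SD 14: Φ((360.5 − 366)/14) = Φ(−0.39) = 35%; on elapsed days Φ((360.5 − 365)/14) = Φ(−0.32) = 37%. With SD 30: 43–44%.
- Day 720: 22–24% (SD 14) or 36–37% (SD 30).
- Day 1096: about 50%.

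**Step 3: hand check at Month 12.** Constant risk of 20% over 36 months gives 1 − 0.8^(1/3) = 7.2% at 12 months and 1 − 0.8^(2/3) = 13.8% at 24. With one third found promptly, no dropout and SD 14, the curve at Day 360 holds about (1/3)(7.2) + (2/3)(7.2)(0.35) = 2.4 + 1.7 = 4.1%. Simulating the SAP rule without dropout gives 3.9–4.2% over SD 14 and 30.

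**Step 4: simulated SAP rule, 50% dropout (%).** One third found promptly and films centred unless stated.

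| Scenario | Month 12 | Month 24 | Month 36 |
|---|---|---|---|
| Truth, constant risk | 7.2 | 13.8 | 20.0 |
| SD 14 | 4.3–4.5 | 11.2–11.3 | 20.0–20.2 |
| SD 30 | 4.7 | 11.7–11.8 | 20.0–20.2 |
| 60% prompt | 5.5–5.7 | | |
| None prompt | 2.8–3.4 | | |
| 30 days late, SD 14 / SD 30 | 2.7 / 3.2–3.3 | | 17.8 / 18.4 |
| 30 days early, SD 14 / SD 30 | 7.1–7.2 / 6.2–6.3 | | 33.1–33.7 / 24.5–24.7 |
| About 90% or more prompt, no discontinuation films | 7.2–7.7 | 14.5–14.9 | |
| Front-loaded 10/2/2% a year (truth 10.0/11.8/13.6) | 6.0–6.5 | 11.8–11.9 | 14.3–14.4 |
| Rising 3/7/11% a year (truth 3.0/9.8 at Months 12/24) | 1.8–2.0 | 6.8–7.4 | |

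A separate simulation of the base case gave 4.2–4.6% at Month 12, so the range is 4.2–4.7%. From rounded figures, 1 − 4.7/7.2 = 35% and 1 − 4.2/7.2 = 42%; unrounded, the lower end is 34%. For 60% prompt, 5.5–5.7% is 20–24% low.

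Month 36 moves both ways because a negative final film removes the patient from the risk set at once. Early final films therefore inflate it and late ones deflate it.

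**Step 5: interval coverage at Month 12 (base case).** With about 450 evaluable, the standard error is about 1.0 point against a bias of 2.6–2.9 points. The nominal 95% interval contains the truth in 21–48% of surveys, across plain and log-log limits (the SAP does not say which). With about 250 evaluable, coverage is 45–54% (plain) or 67–75% (log-log). At Month 36 with about 450 evaluable it is about 92–95%.

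**The case against.** **The size rests on inputs that the documents do not give.** This stands. Only the mismatch of days comes from the text.

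**Suspected fractures are filmed when they arise, so few may be silent.** This stands as a condition. A reader might infer that Month 12 is always low, or that Month 24 is always low under constant risk. The documents support neither: they give no share found by symptoms, and at about 90% or more found promptly with discontinuers not filmed, both shortfalls disappear or reverse. That case also departs from Protocol 9.2.5, which asks for a film at discontinuation.

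**Perhaps 12 months means 360 days.** This fails. The SAP reads Month 36 at Day 1096, not 3 × 360 = 1080.

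**The consequence is limited.** This largely stands. The objective is 36-month treatment, and the fracture endpoint has no test or comparator. The SAP defines its time as time to the diagnosing film and prints numbers at risk, events and censored patients. The Month 18 row picks up most on-time 12-month films: 9.1% against a true 10.4% in the base case, about 12% low. None of this corrects the row labelled Month 12 or its interval.

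**Poor coverage depends on the number evaluable.** This stands. It should be quoted as a range over that number, not as one figure.

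**Conclusion.** The defect is real and conditional, and it should be fixed. The read-outs at Days 360 and 720 precede the due films for every possible start date, and no rule in 5.4 or 5.5 repairs this.

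- **Month 12** is too low when films centre on or after the due date and a material share of fractures is silent until the scheduled film: about 34–42% low with one third found promptly, about 20–24% with 60%. Films about 30 days early shrink or remove the shortfall, and the high-detection case without discontinuation films removes or reverses it.
- **Month 24** is usually low under constant or rising risk (15–19% low in the base case), but not under heavily front-loaded risk with 50% dropout or in the same high-detection case.
- **Month 36** is near the truth for centred films. A reader might infer that the 36-month result or some decision is undermined; the documents do not support that. The harm is to the reported early course and its confidence interval.

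The direction under these conditions is secure. The sizes hold only for the assumed film timing and scatter, fracture rate and prompt share.

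**What to change.** Report 12-, 24- and 36-month incidence from an interval-censored estimate on (last negative film, first positive film], for example Turnbull or piecewise exponential. State that symptom-triggered films make inspection times partly informative.

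Alternatively, assign scheduled films to their due visit (Days 271–450, 631–810, 991–1170) for both event and censoring, and read at the calendar due day. Keep suspected-fracture and discontinuation films at their own dates, so that no film is left unassigned.

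Either way, state the day count, align the 6.3.3 ranges with the same rule, and keep the raw-date Kaplan-Meier as supportive, labelled as time to detection. Do not simply move the read-out: with centred films, Days 390/750/1126 give 7.7/14.6/32.0% (SD 14) or 6.7/13.6/24.4% (SD 30) against 7.2/13.8/20.0%.

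The cost is SAP wording and some re-programming; film dates are already collected. A small upward bias remains. Over film centres from 30 days early to 30 days late, with one third or 60% prompt, the interval-censored fit gave 7.2–8.3/14.0–15.2/19.9–21.3% (up to about 8.5% at Month 12 in another run). Window grouping gave 7.4–8.9/14.1–16.1/19.7–22.3%, and 8.5–9.3% at Month 12 when 80–100% were prompt and half or none of the dropouts were filmed. In a run at 10% a year with one third found clinically and all discontinuers filmed, dating scheduled films to their visit gave 10.5/20.1% and the interval-censored fit 10.0/19.1%, against 10.0/19.0% at Months 12/24.

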6.3.2. Incidence of Non-vertebral Fracture

| | |
|---------------------|---|
| 1) Analysis set | Patients evaluated for efficacy |
| 2) Chart plan | Table 3-2-1 Table 3-2-2 Table 3-2-3 Table 3-2-4 |
| 3) Analysis items | Non-vertebral fracture Non-vertebral fracture <non-traumatic> Femur fracture Femur fracture <non-traumatic> |
| 4) Analysis methods | Non-vertebral fracture will be analyzed in the same manner as described in Section 6.3.1, “Incidence of Vertebral Fracture.” The time to the first onset of the analysis item is defined as time from the start date of Benet/Actonel treatment to the earliest date of diagnosis of the analysis item. Patients with no analysis item will be censored at the latest date of dosing, discontinuation, assessment of each efficacy endpoint, or onset/outcome of AE. |

6.3.3. Incidence of Vertebral Fracture Event at Each Time Point of Assessment

| | |
|---------------------|--|
| 1) Analysis set | Patients evaluated for vertebral fracture |
| 2) Chart plan | Table 3-3-1 Table 3-3-2 |
| 3) Analysis items | New vertebral fracture or worsening of prevalent fracture New vertebral fracture or worsening of prevalent fracture <non-traumatic> |
| 4) Analysis methods | The number of relevant patients, observed person·years, number of patients with the first onset of the analysis item, and incidence rate (number of patients with event/100 person·years) in the range of assessment at each time point of assessment (see below) will be calculated, and the ratio of incidence rate at each time point of assessment relative to Month 6 and its 95% confidence interval will be calculated. Handling of onset day of the analysis item and data for analysis will be as specified in Section 6.3.1, “Incidence of Vertebral Fracture.” |

Observed person·years: (1)+2)) ÷ 12

1): (Number of patients with radiography, no event, and no censoring in the range of assessment at each time point of assessment) \times 6

A patient with no radiography at the relevant time point of assessment, but with valid radiography at any later time point will be counted at the relevant time point of assessment.

2): Total time (months) from the start date of assessment to event or censoring in the range of assessment at each time point of assessment for patients with event or censoring

Incidence rate: (number of patients with event \div observed person-years) \times 100

Range of assessment at each time point of assessment

| Time point of assessment | Range of assessment |
|--------------------------|---------------------|
| Month 6 | Days 2 to 180 |
| Month 12 | Days 181 to 360 |
| Month 18 | Days 361 to 540 |
| Month 24 | Days 541 to 720 |
| Month 30 | Days 721 to 900 |
| Month 36 | Days 901 to 1096 |

No radiographic data collected after the end date of Benet/Actonel treatment + 90 days or after 3 consecutive months (90 days) of interruption in patients with interruption of treatment will be handled as data in the range of assessment (not used for analysis).

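### Vertebral fracture rate ratios are referred to Month 6 (Days 2 to 180), a period with no calendar film, so a constant fracture rate appears as raised ratios in later bins

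*SAP*

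**What the plan says.** Protocol 9.2.5 places vertebral fracture assessments after baseline at "12, 24, and 36 months after the start of treatment (or discontinuation of treatment), and when vertebral fracture is suspected". No calendar film falls before Month 12.

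SAP 5.1 Section 6.3.1 dates an event at "the earliest date of radiography with a diagnosis of the analysis item". For the rest, "Patients with no analysis item will be censored at the latest date of radiography with no evidence of the analysis item". Section 6.3.3 adopts these rules.

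Section 6.3.3 defines six bins, of which the first, Month 6, is Days 2 to 180. A patient adds six months to a bin if he or she belongs to the "Number of patients with radiography, no event, and no censoring in the range of assessment". It adds: "A patient with no radiography at the relevant time point of assessment, but with valid radiography at any later time point will be counted". Finally, "the ratio of incidence rate at each time point of assessment relative to Month 6 and its 95% confidence interval will be calculated". No method is named for that interval. The last bin is "Days 901 to 1096".

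**The concern.** The numerator and denominator of the Month 6 rate follow different clocks. Person-time is credited to the half-year in which it was lived. That is right for a patient later shown to be free of fracture. Events are credited to the half-year in which a film was taken. A fracture that arises in the first six months without raising suspicion waits for the next film, normally the 12-month one, and leaves the reference bin.

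The 12-month film also sits on a bin edge. Day 360 belongs to Month 12, but the calendar anniversary, Day 366, belongs to Month 18. Likewise Day 720 belongs to Month 24 and Day 731 to Month 30. A few days' difference in clinic practice therefore decides which bins are raised.

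At stake is the reading of Tables 3-3-1 and 3-3-2. An unchanged fracture rate would appear as an elevated or sawtooth pattern after Month 6, with 95% confidence intervals attached, and could be taken for waning effect.

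There are two smaller faults. The Month 36 bin is longer than the six months it is credited. Films after Day 1096 fall in no bin, although they can be valid under the rule of end of treatment plus 90 days, and the SAP does not clearly say whether such patients keep their Month 36 person-time.

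**Working it through.** **The plan's own figures.** The documents give no expected fracture rate, event count or ratio for Section 6.3.3. The only related figure is the sample size in Protocol 3.2, 250 / (1 - 0.50) = 500. It reproduces but does not bear on this point.

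**Inputs from the documents.** Film schedule (Protocol 9.2.5); event and censoring dates (SAP 6.3.1); bins and person-year formula (SAP 6.3.3); 30-day months (the treatment-duration definition in SAP 5.5); 50% dropout (Protocol 3.2).

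**Assumptions.** Share s of fractures filmed promptly, 0.33 to 0.95; 36-month incidence 10% to 30%; constant hazard; a film at every discontinuation, as Protocol 9.2.5 schedules.

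**Closed form** (no dropout, films on exact days, rate L per year):

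- Month 6 bin, events per patient: 0.5 × s × L.
- Bin holding the routine film: its own promptly filmed fractures, 0.5 × s × L, plus the unfilmed fractures of the whole year, (1 - s) × L.
- Person-time is equal, so ratio = (0.5s + 1 - s) / (0.5s) = (2 - s) / s.
- s = 0.33: 0.835 / 0.165 = 5.06. s = 0.6: 0.7 / 0.3 = 2.33. s = 0.8: 0.6 / 0.4 = 1.50. s = 0.95: 0.525 / 0.475 = 1.11. s = 1: 1.00.

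**Simulation** (400,000 patients per setting, 50% exponential dropout). Films were placed on anniversaries (Days 366, 731, 1097) or nominal days (360, 720, 1096), exact or scattered by ±30 days. The ratio and share columns cover 10-30% incidence. The last column uses 500 patients, 20% incidence, 2,000 repeats and Wald intervals on the log rate ratio.

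| s | Share of fractures arising in Days 2-180 that Month 6 counts | Ratio, film-bearing bins, exact days | Ratio, all five bins, ±30 days | At least one of five 95% CIs wholly above 1 |
|---|---|---|---|---|
| 0.33 | 36-37% | 4.4-5.1 | 2.3-3.9 | 96-100% |
| 0.6 | 62% | 2.2-2.5 | 1.4-2.1 | 63-83% |
| 0.8 | 81-82% | 1.5-1.6 | 1.1-1.4 | 30-39% |
| 0.95 | 95% | 1.1-1.15 | 1.0-1.1 | 12-14% |
| 1 (control) | all | 0.96-1.05 (Months 12-30) | 0.96-1.05 (Months 12-30) | 9-11% |

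Bins without routine films stay at 1.0-1.3 when films fall on exact days. In the control, Month 36 is 0.98-1.11.

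Example, s = 0.33 and 20% incidence:

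| Film timing | Month 12 | 18 | 24 | 30 | 36 |
|---|---|---|---|---|---|
| Anniversaries | 1.2 | 5.1 | 1.2 | 5.1 | 1.3 |
| Nominal days | 4.6 | 1.0 | 4.6 | 1.0 | 4.4 |
| ±30-day scatter | 2.6 | 3.5 | 2.3 | 3.9 | 2.9 |

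**Sensitivity to dropout.** At 26.7%, the rate Protocol 3.2 gives for the earlier study, film-bearing bins with exact-day films show 4.7-5.3, 2.3-2.5, 1.5-1.6 and 1.1 (20% incidence). The result does not depend on the 50%.

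**Secondary points.** The Month 36 bin has 1096 - 901 + 1 = 196 days; 196 / 180 = 1.089, an error of at most 8.9%. Events detected after Day 1096 are 1-15% of the total with anniversary films, 1-8% with scatter, and none if films are taken by Day 1096. With scatter and s = 0.6, the Month 36 ratio is 1.7-1.8 if patients filmed after Day 1096 keep their person-time and 3.1-3.3 if they do not.

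**The case against.** **The table is minor.** Protocol 10.6 asks for number, proportion and cumulative incidence, not these ratios. There is no control arm, no p-value and no decision rule. The bias runs against the product, and the Kaplan-Meier curve in SAP 6.3.1 would show steps at the yearly films. All of this stands and limits the importance. It does not make the ratios correct.

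**The size is assumed.** The share s appears nowhere in the documents, and at 0.95 the excess is negligible. Low back pain is also recorded at Months 3 and 6 (Protocol 9.2.7), which could prompt films inside the reference bin. This stands as a caveat on size. Yearly films compared with baseline are, however, designed to find fractures that prompted no visit.

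**Discontinuation films may not be taken.** With none at all (20% incidence, 50% dropout), nominal-day ratios fall to about 2.0, 1.33 and 1.0 for s = 0.6, 0.8 and 0.95, while anniversary ratios do not fall (about 2.5 at s = 0.6). Months 12 and 24 drop to 0.85-0.91 with anniversary films. Under scatter at s = 0.95, Months 12 and 24 are 0.96 and 0.94. The stated ranges therefore hold only with the scheduled discontinuation film.

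**The analysed set is smaller than 500.** With 250, a deliberately low case, the chance of at least one interval above 1 is about 68-89%, 37-56% and 17-24% for s = 0.33, 0.6 and 0.8. It is lower, but still well above the 9-11% control, which was computed with 500 patients.

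**Films after Day 1096 may be covered** by the sentence on valid radiography at a later time point. That reading is possible, but no time point after Month 36 is defined, so the text should say so.

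**The change is late.** Ratios to Month 6 date from SAP version 4.0, and version 5.1 is dated November 2017. This is a reason to document the change.

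**Conclusion.** The point holds. Whenever some fractures are not filmed promptly, the Month 6 rate is too low and the ratios are raised in bins that receive routine films, although the true ratio is 1.0. Which bins these are depends on film timing: Months 18 and 30 on anniversaries; Months 12, 24 and 36 on nominal days; all five with ordinary scatter, apart from values close to 1 at s = 0.95.

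The direction follows from the documents. The size rests on the assumed s and on a film at discontinuation: roughly fivefold at s = 0.33, about 1.5 at s = 0.8, negligible at s = 0.95. The return to about 1 in Months 12-30 at s = 1 shows that detection timing is the cause.

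This should be fixed. It does not threaten the primary cumulative incidence estimate.

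**What to change.** In SAP 6.3.3, replace the six half-year bins with three film-to-film intervals: baseline to Month 12 film, Month 12 to Month 24 film, Month 24 to Month 36 film.

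- Take as scheduled film the one nearest Day 360, 720 or 1096 within Days 271-450, 631-810 or 991-1170, the windows SAP 5.4 already uses for bone mineral density.
- Assign films for suspected fracture or discontinuation to the interval in which they fall.
- Compute person-years as actual days from interval start to next film, event or censoring, divided by 365.25. This also removes the Month 36 length error, and the Month 36 window takes in films up to Day 1170.
- Report ratios relative to year 1 and name the interval method, for example Wald on the log rate ratio.
- Where a scheduled film is missing, split at the nominal day and report how many patients this affects.

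Under a constant rate with no missed films, the yearly ratios are 0.96-1.03, and at least one of the two intervals lies above 1 in 3.6-5.5% of trials.

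The cost is SAP wording and programming, with the table layouts to match; no new data are needed. Half-year resolution is lost. A small bias remains when films are missed. With 10% of Month 12 and 24 films missed, ±30-day scatter and 20% incidence:

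| s | Year 2 ratio | Year 3 ratio | Current rule, same data |
|---|---|---|---|
| 0.33 | 1.07-1.09 | 1.15-1.17 | 2.3-3.9 |
| 0.6 | 1.04-1.05 | 1.09-1.10 | 1.4-2.0 |
| 0.8 | 1.03 | 1.05-1.06 | 1.2-1.4 |
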